Health services utilization and medication use following index hospitalization will be collected based on self-reports. For the purposes of the analyses, hospital and emergency department admissions will be categorized as: 1) hospitalization/emergency department visits related to the original index injury admission, 2) hospitalization and emergency department visits related to a new injury, and 3) a non-injury related hospitalization (e.g., hospitalization for a chronic medical condition such as congestive heart failure).

Costs of intervention are likely to be dwarfed by the total costs of post-injury care, which would make it difficult to estimate the incremental costs of intervention precisely, given our sample size. This is mainly because our prior investigations suggest that up to 15-20% of injured trauma survivors in both intervention and control conditions experience recurrent injury emergency department and hospital admissions related to the index injury event, increasing the variance of the cost estimators. We will therefore provide detailed impact inventory for the intervention to identify specific components of total costs. Also of relevance, preliminary studies by the investigative group suggest that emergency department and hospital admissions for a new injury are policy relevant outcomes that are potentially malleable by care management interventions targeting PTSD and related comorbidity.^{11,55,220}

3. Costing procedures

The following categories of costing information will be collected: 1) total charges for the index injury visit will be extracted either from the hospital trauma registry or the hospital EHR as available across the 24 level I trauma center sites, 2) all follow-up hospital, emergency department, and outpatient visits and re-hospitalizations over the course of the 12-months after the injury will also be collected from patient 3-, 6-, and 12-month self-report data or from the trauma registry, 3) structured patient interviews will be used to assess medication use.

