All units of service will be assigned standard procedure codes (e.g., *Current Procedural Terminology, Fourth Revision* codes) for procedures, Diagnostic Related Groups (DRGs) for hospitalizations, and National Drug Codes for prescribed medication.³²³ These codes will be converted into costs by using the Medicare reimbursement fee schedule for 2014. We will employ a validated and standardized program, EZ Fees 2014 http://www.rbrvs.net/, in this procedure.³²⁴ The EZ Fees program has the 2014 Medicare fee schedule and is frequently updated as payment changes. For services not covered by Medicare, we will use the prevailing fees available from aggregate hospital data at http://hrsa.dshs.wa.gov/rbrvs./. These codes will be translated into unit prices using the Resource Based Relative Value Scales underlying Medicare payment rates for visits of different types, using EZ Fees http://www.rbrvs.net/. Medication costs will be ascertained using the Federal Supply Schedule for a given medication based on its NDC code.³²⁵ All costs will be converted to 2018 using the PHC and PCE indices http://meps.ahrq.gov/about_meps/Price_Index.shtml.

Effectiveness/utility assessments. Exploratory analyses of cost-effectiveness will be conducted only if we find robust treatment effects for PTSD and comorbidity. Gold et al. have suggested the use of generic preference-based utility measures for cost-effectiveness analyses for comparability.²¹⁷ However, because of the unique characteristics of psychiatric populations, mental health services researchers frequently employ disease specific effectiveness measures.^{221,224,326} The study team may explore a series of policy relevant effectiveness measures. The study team may use a method employed in a number of mental health effectiveness trials^{221,224,326} to derive a disease specific clinical outcome entitled "PTSD-free days." The investigative team will also use the Time Trade-Off procedure to estimate health-related quality of life weights longitudinally, which could be used to calculate Quality of Life Adjusted Years (QALYs). Finally, the investigation may also employ the MOS SF-12, to ascertain a generic preference-based utility estimate that has been previously used with injured patients in prior study team investigation.^{243,262,327-329}

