Cost analyses. The investigation's exploratory cost analysis will first compare total costs for patients in the intervention and control conditions; total costs will be the primary dependent variable for this analysis. Total costs include the costs of the intervention, medication and health service utilization (i.e., inpatient, skilled nursing facility, emergency room, and outpatient utilization). After the total cost comparison is completed, other exploratory analyses will compare intervention and control costs restricted to intervention costs and costs of emergency department and hospital admissions. Randomization should ensure balance between the two groups in pre-injury utilization. So, our primary analyses will be to study incremental costs, effectiveness and cost-effectiveness without any adjustments. As a sensitivity analysis the study team will examine patient self-report data to assess balance between the two and to determine if adjustments are necessary. If adjustments become necessary, we will use non-parametric methods previously employed by Drs. [name] and [name].^{135,224} The choice of non-parametric methods, such as propensity score weighting, is mainly because of the sample size of our analyses, where complicated regression models will be difficult to fit. Standard errors and 95% confidence intervals for incremental costs, effectiveness and cost-effectiveness will be obtained using

clustered bootstrapping.224,330,331

A. Study Governance

The study organizational structure and governance plan aims to simultaneously optimize diverse stakeholder input into the trial design and implementation while maintaining the proposed study timeline and UH3 milestone completion. The study organizational structure is outlined in Figure 17.

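### A bootstrap standard error and interval for cost-effectiveness, if this means the ratio, is reliable only when the effect difference is clearly non-zero; net monetary benefit would avoid the problem

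*Combined protocol and SAP*

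**What the plan says.** All of this is in section E, Exploratory Health Economic Evaluation.

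- **Uncertainty (Cost analyses).** "Standard errors and 95% confidence intervals for incremental costs, effectiveness and cost-effectiveness will be obtained using" "clustered bootstrapping". The type of bootstrap interval is not given. The comparison is unadjusted: "our primary analyses will be to study incremental costs, effectiveness and cost-effectiveness without any adjustments".
- **Expected precision (2. Approach to cost analyses).** Total post-injury costs are expected to swamp the cost of the intervention, "which would make it difficult to estimate the incremental costs of intervention precisely, given our sample size". The reason given is that up to 15-20% of patients in both conditions "experience recurrent injury emergency department and hospital admissions related to the index injury event, increasing the variance of the cost estimators".
- **Condition (Effectiveness/utility assessments).** "Exploratory analyses of cost-effectiveness will be conducted only if we find robust treatment effects for PTSD and comorbidity". Robust is not defined.
- **Denominator (same paragraph).** It is left open among PTSD-free days, QALYs from Time Trade-Off weights and an SF-12 utility.

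The section names no net-benefit analysis, acceptability curve, cost-effectiveness plane or Fieller interval.

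**The concern.** A ratio of two estimated differences behaves badly in two ways.

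1. Replicates with an effect difference near zero give enormous ratios, and a few of them determine the bootstrap standard error. If the effect difference can also change sign, a negative ratio may mean cheaper and better or dearer and worse.
2. Within the cheaper-and-better quadrant the ratio does not rank outcomes by merit. Saving $1,000 while gaining 0.10 QALY gives -1,000/0.10 = -10,000. Saving $1,000 while gaining only 0.02 QALY gives -1,000/0.02 = -50,000. The worse result has the more extreme ratio.

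At stake is how uncertainty is described in an exploratory analysis that the protocol intends as a contribution to national policy discussion. The primary PTSD test is not involved.

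**Working it through.** **Precision of the PTSD effect, from the plan's own figures.** The economic section gives no precision, so I started from Table 10 (Sample size and power). The Hussey-Hughes variance is

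Var = I·s²(s² + T·t²) / [(IU − W)s² + (U² + ITU − TW − IV)t²]

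with I = 24 sites, T = 5 periods, four steps, U = 60, W = 1,080, V = 180, s² = (1 − ICC)/6 and t² = ICC. The 6 is 30 completers over 5 periods. At ICC 0.02:

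- Var = 24 × 0.1633 × (0.1633 + 0.10) / (360 × 0.1633 + 1,080 × 0.02) = 1.032/80.4 = 0.01284.
- With the baseline factor 1 − 0.7² = 0.51, SE = √(0.01284 × 0.51) = 0.0809.
- Minimum detectable effect = (1.960 + 0.842) × 0.0809 = 0.227.

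Across ICC 0.005, 0.010, 0.020 and 0.030 this gives 0.216, 0.220, 0.227 and 0.231, which is Table 10 exactly.

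Using the 0.23 of Table 11, SE = 0.23/2.802 = 0.082. An observed effect of 0.23 then has z = 2.80, and the previously observed 0.34 has z = 0.34/0.0821 = 4.14.

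**Replicates of the ratio.** Cost and effect differences are taken as independent normals, each with unit SE. The documents give no cost SD, so cost z is assumed to be 0 to 1.

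- Dearer and worse: Φ(cost z) × Φ(−effect z). At effect z = 1 this is 0.50 × 0.159 = 7.9% for cost z = 0, and 0.841 × 0.159 = 13.3% for cost z = 1.
- Cheaper and better: Φ(−cost z) × Φ(effect z). At the two larger effect sizes this is about 50% for cost z = 0 and 16% for cost z = 1.

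The limits and standard errors below come from 2,000,000 draws at cost z = 0, in units of SE(cost)/SE(effect). The standard error is taken over repeated sets of 1,000 replicates.

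| Effect z | Dearer and worse (cost z 0 to 1) | 95% percentile limits | SE of ratio: median (5-95% range) |
|---|---|---|---|
| 1.00 | 7.9-13.3% | −7.7 to 7.7 | 21 (7.8 to 230) |
| 1.96 | 1.3-2.1% | −2.2 to 2.2 | 5.4 (2.0 to 59) |
| 2.80 | 0.13-0.21% | −0.97 to 0.97 | 0.87 (0.51 to 8.3) |
| 4.14 | about 0 | −0.54 to 0.54 | 0.27 (0.26 to 0.30) |

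With 2,000 replicates per run, the standard error at z = 2.80 still ranges from about 0.6 to 12.

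**The tails.** A 95% limit lies in the outer 2.5%, so small shares matter. At effect z = 1.96, dearer-and-worse replicates make up about a quarter of the lower 2.5% tail at cost z = 0 and about 69% at cost z = 1.

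**Ordering.** I took pairs of cheaper-and-better replicates in which one beats the other on both cost and effect. The ratio ranks them wrongly in about a quarter of pairs at z = 2.80 and about one in six at z = 4.14.

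**Net monetary benefit.** NMB = λ × effect difference − cost difference has no denominator. With λ at one unit of SE(cost)/SE(effect), its SE is √(1 + 1) = 1.41 at every effect z. Over runs of 2,000 replicates its relative error is about 1/√(2 × 2,000) = 1.6%.

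**The case against.** A reader might infer that, because the plan expects imprecise incremental cost, the interval is bound to mix cheaper-and-better with dearer-and-worse results and cannot be read. The documents do not support that. Imprecise cost alone only moves replicates between dearer-and-better and cheaper-and-better. Dearer-and-worse replicates require the effect difference to change sign. The plan's condition limits this for a PTSD-based denominator: at most about 2% of replicates if the effect is just significant, about 0.2% at the design effect and practically none at 0.34. When every replicate has a positive effect, a ratio below a positive λ is the same statement as positive net benefit, so a positive upper limit keeps its meaning. That objection stands.

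It is also fair to say that:

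- the plan never uses the word ratio, and the references cited for the method could not be consulted;
- the work is labelled exploratory, and total cost is its primary dependent variable;
- the plan already answers imprecise cost with an itemised impact inventory and restricted cost comparisons;
- cost findings are said not to have dominated past policy discussions.

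Three things remain. The condition concerns PTSD and comorbidity, while the denominator may be a QALY or SF-12 utility difference whose precision is nowhere stated. The instability of the standard error extends to the trial's own design effect. The ordering defect does not depend on the effect changing sign, so no condition on effect strength removes it.

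**Conclusion.** The concern holds in conditional form. The bootstrap standard error of the ratio is unstable at effect z of about 1 to 2.8, and settles only near 4.14. Dearer-and-worse contamination is material for a weakly estimated denominator (8-13% at z = 1) and can dominate one tail at z = 1.96, but is rare from z = 2.80 upwards. If cost is near zero, 16-50% of replicates are cheaper and better, and there the size of a negative ratio says nothing dependable about merit.

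These figures rest on normal, independent replicates and an assumed cost z of 0 to 1. The z values of 2.80 and 4.14 belong to the adjusted PTSD symptom score. The unadjusted economic effect is a different estimate, and neither PTSD-free days nor QALYs has a stated precision. No dollar value for the ratio's standard error can be given, because the documents supply no cost or QALY SD. Nor do they support saying that the economic findings as a whole would be arbitrary. This is a worthwhile improvement to an exploratory analysis.

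**What to change.** In the Cost analyses paragraph of section E:

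1. Report the cost-effectiveness ratio as a point estimate, without a bootstrap standard error.
2. Base uncertainty on incremental net monetary benefit over a stated range of willingness-to-pay values, with 95% CIs from the same clustered bootstrap.
3. Show the replicates on the cost-effectiveness plane, with an acceptability curve.

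The cost is a change of SAP wording and a few lines of code, with the same data and the same bootstrap. The one drawback is that willingness-to-pay values must be stated in advance; values per PTSD-free day have to be shown as a range.
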